I agree to maintain the confidentiality of all information received or developed in connection with this protocol.

Investigational Site Name: _____

Print Investigator Name: _____

Investigator Signature: _____ Date: _____

SUMMARY OF CHANGES

The following sections have been changed in Amendment 1 of the ARQ-151-313 protocol:

Version/Date	Description
December 20, 2020	Original Protocol
Amendment 1 September 17, 2021	
Added Summary of Changes section.Added statement that during the conduct of the study, additional countries and/or sites may be added if necessary.Sample size increased from approximately 400 to approximately 1500 subjects to allow:
All subjects from ARQ-151-315 to enroll into the ARQ-151-313 Open Label Extension study.An additional ~275 subjects ages 6-17 from ARQ-151-311 and additional ~275 subjects ages 6-17 from ARQ-151-312 to enroll into the ARQ-151-313 Open Label Extension study for a 24-week treatment period. This is Cohort-Week 24.Clarification added that if an unscheduled visit is required for reasons other than safety, the following assessments are not required:
vIGA-AD and EASIBSA affected with ADLocal tolerability assessment (by Investigator)Removed all safety labs for subjects ages 2-11; safety labs would have been evaluated at screening in the preceding study and the investigator may order safety labs at any time during the study to evaluate an adverse event.WI-NRS:
Added statement that caregiver/parents will be given instructions on how to complete this questionnaire for subjects between 2 and 5 years of age.Added that parent and/or guardian will be trained at the baseline visit to assist the subject, if needed, in the accurate completion of the WI-NRS for subjects \geq 6 years of age.Added clarification that only subjects 18 years and older will be enrolled at sites located in the province of Québec in Canada.

Version/Date	Description
	
• Added PK draw at Week 52/ET for subjects \geq 12 years of age.• Updated exclusion criterion 5 and Figure 1 to note that subjects who have undergone a bilateral tubal ligation/occlusion are considered females of childbearing potential using a highly effective method of contraception.• Updated the language of endpoints to be consistent with other Arcutis study protocols• Added secondary endpoint: vIGA-AD success (defined as Viga-AD value of 0 or 1 plus a 2-grade improvement from baseline)• Removed some of the analyses and will add the details into SAP.
– For the analysis for WI-NRS and EASI, the analysis changed to summary by visits overtime which includes change and percent change from baseline.– Removed the following duplicate sections: Adverse Events: The subject incidence of treatment-emergent adverse events (TEAE) will be summarized overall, by severity, and by attribution. Clinical Laboratory Results: Shifts in clinical laboratory parameters from baseline to worst post-baseline grade will be provided.• Moved the vital signs in Section 6.6 to Section 6.9.

TABLE OF CONTENTS

1.	PROTOCOL SUMMARY.....	13
1.1.	Synopsis.....	13
1.2.	Study Schema	18
1.3.	Schedule of Visits and Assessments.....	19
2.	INTRODUCTION	23
2.1.	Background.....	23
2.2.	Nonclinical Studies	24
2.3.	Clinical Studies.....	24
2.3.1.	Topical Roflumilast Cream.....	24
2.3.2.	Oral Roflumilast Tablet	29
2.4.	Rationale for Development.....	29
2.4.1.	Dose Selection	30
2.4.2.	Risks and/or Benefits to Subjects	30
3.	STUDY OBJECTIVES AND ENDPOINTS.....	31
3.1.	Study Objectives.....	31
3.1.1.	Primary Objective.....	31
3.2.	Study Endpoints.....	31
3.2.1.	Primary Endpoints	31
3.2.2.	Secondary Endpoints	31
4.	INVESTIGATIONAL PLAN.....	32
4.1.	Overall Study Design and Plan.....	32
4.2.	Number of Study Sites and Subjects	33
4.3.	Subject Participation	33
4.4.	Numbering of Subjects	33
4.5.	Selection of Study Population	33
4.5.1.	Inclusion Criteria	33
4.5.2.	Exclusion Criteria	34
4.6.	Study Restrictions.....	35
4.6.1.	Prohibitions and Concomitant Therapy	35
4.7.	Treatment.....	37

4.7.1.	IP Supplies, Packaging and Labeling	37
4.7.2.	Blinding	37
4.7.3.	Treatment Administration.....	37
4.7.4.	Treatment Compliance.....	38
4.7.5.	Removal of Subjects from Study Treatment	39
4.7.6.	Removal of Subjects from the Study	39
5.	STUDY PROCEDURES	40
5.1.	Safety Assessments.....	40
5.1.1.	Day 1 Visit.....	40
5.1.2.	Contraception Requirements	41

APPENDIX 12. NIAID DMID TOXICITY TABLE84

LIST OF TABLES

Table 1:	ARQ-151-101: Skin Toleration Treatment-Emergent Adverse Experiences	25
Table 2:	Excluded Medications and Treatments.....	36
Table 3:	Laboratory Tests	42

LIST OF FIGURES

Figure 1.	Contraception Requirements for Female Subjects	41
-----------	--	----

LIST OF ABBREVIATIONS AND DEFINITIONS OF TERMS

Abbreviation	Definition
α	Alpha Level (significance level)
AE	Adverse Event
AMP	Adenosine Monophosphate
AD	Atopic Dermatitis
AUC	Area Under the Curve
BSA	Body Surface Area
CDI	Children's Depression Inventory
CDLQI	Children's Dermatology Life Quality Index
C_{\max}	Maximum Concentration
cm	Centimeter
COPD	Chronic Obstructive Pulmonary Disease
CRF	Case Report Form
C-SSRS	Columbia-Suicide Severity Rating Scale
CTCAE	Common Terminology Criteria for Adverse Events
DFI	Dermatitis Family Impact
DLQI	Dermatology Life Quality Index
EASI	Eczema Area and Severity Index
FDA	U.S. Food and Drug Administration
FOCBP	Female of Child Bearing Potential
FSH	Follicle-Stimulating Hormone
GCP	Good Clinical Practices
GLP	Good Laboratory Practices
hr	Hour
IB	Investigator's Brochure
IC_{50}	Half Maximal Inhibitory Concentration
ICF	Informed Consent Form
ICH	International Conference on Harmonisation
ID	Identification
IGA	Investigator Global Assessment
IL	Interleukin

Abbreviation	Definition
IND	Investigational New Drug
IP	Investigational Product
IRB	Institutional Review Board
IWRS	Interactive Web Response System
kg	Kilogram
LED	Light Emitting Device
µg	Microgram
MedDRA	Medical Dictionary for Regulatory Activities
mg	Milligram
min	Minute
mL	Milliliter
MTD	Maximum Tolerated Dose
NCI	National Cancer Institute
NIH	National Institutes of Health
NOAEL	No Observed Adverse Effect Level
ng	Nanogram
P-450	Cytochrome P450
PDE-4	Phosphodiesterase 4
PDMP	Protocol Deviation Management Plan
PHQ-8	Patient Health Questionnaire-8
PI	Principal Investigator
PK	Pharmacokinetics
POEM	Patient-Oriented Eczema Measure
QD	Once Daily ("quaque die")
SAE	Serious Adverse Event
SAP	Statistical Analysis Plan
SCORAD	Scoring Atopic Dermatitis
SD	Standard Deviation
SUSAR	Suspected Unexpected Serious Adverse Reaction
TCPS	Tri-Council Policy Statement

Abbreviation	Definition
TEAE	Treatment Emergent Adverse Event
T _{max}	Time to Reach Maximum Concentration
US	United States
vIGA-AD	Validated Investigator Global Assessment-Atopic Dermatitis
WI-NRS	Worst Itch – Numeric Rating Score

1. PROTOCOL SUMMARY

1.1. Synopsis

Name of Sponsor/Company: Acutis Biotherapeutics, Inc.		
Name of Investigational Product: ARQ-151 will be supplied as an emollient cream at 0.15% or 0.05% strength		
Name of Active Ingredient: Roflumilast, a PDE-4 inhibitor		
Protocol Number: ARQ-151-313	Phase: 3	Country: US and Canada
Title of Study: A Phase 3, Multicenter, Open-Label Extension Study of the Long-Term Safety of ARQ-151 Cream 0.15% and ARQ-151 Cream 0.05% in Subjects with Atopic Dermatitis		
Clinical Indication: Atopic Dermatitis		
Number of Sites: Up to approximately 120 study sites in the United States and Canada. During the conduct of the study, additional countries and/or sites may be added if necessary.		
Study Population: Up to approximately 1500 subjects that have completed the 4-week treatment period in studies ARQ-151-311 or ARQ-151-312 or ARQ-151-315 and are willing and qualified to enroll in this long-term extension study will receive ARQ-151 cream 0.15% (ARQ-151-311/312 roll-overs) or ARQ-151 cream 0.05% (ARQ-151-315 roll-overs) QD. Subjects 6-17 years of age enrolled under Amendment 1 will be treated for 24 weeks with ARQ-151 cream 0.15% (Cohort-Week 24). Subjects on ARQ-151 cream 0.05% who turn 6 years old during ARQ-151-313 will switch to ARQ-151 cream 0.15% at their first scheduled post-birthday visit.		
Objectives:		
Primary: To assess long-term safety in a multicenter, open-label, single-arm study in subjects with atopic dermatitis treated with ARQ-151 cream 0.15% QD (subjects \geq 6 years of age) or ARQ-151 cream 0.05% QD (subjects 2 to 5 years of age) after completing one of three Phase 3 studies (ARQ-151-311, ARQ-151-312, or ARQ-151-315).		
Summary of Study Design: ARQ-151-313 is an open-label, single-arm, long-term safety study of ARQ-151 cream 0.15% and ARQ-151 cream 0.05% in subjects with atopic dermatitis. Eligible subjects will enroll into the long-term safety study on the same day as the Week 4 visit of the preceding study (ARQ-151-311, ARQ-151-312, or ARQ-151-315). Study medication will be applied topically for up to 24 (Cohort-Week 24) or 52 weeks at home. All affected areas, except on the scalp, will be treated. For the first 4 weeks of study ARQ-151-313, all subjects will apply study medication QD in the areas identified and treated as per the body diagram in the preceding study (ARQ-151-311/312/315). Beginning at the Week 4 visit, any subject who achieves vIGA-AD of '0-clear' as confirmed by the Investigator at a scheduled or unscheduled clinic visit, will switch to twice weekly (BIW) maintenance treatment. For maintenance therapy, study medication will be applied on two nonconsecutive days per week (e.g. Monday and Thursday) to areas commonly and/or most recently affected by AD, and any		

areas where AD is developing. Subjects receiving maintenance treatment who experience AD worsening (signs and symptoms) for 1 week despite dosing twice weekly will phone the clinical study site, resume daily dosing, and complete the subject diary accordingly. The phone call (but not a clinic visit) is required to resume daily dosing. At clinic visits, subjects receiving maintenance treatment may continue twice weekly maintenance dosing if vIGA-AD is either '0-clear' or '1-almost clear'. Subjects will resume daily dosing if vIGA-AD ≥ 2 , and can resume daily dosing if signs/symptoms of AD are not adequately controlled with maintenance therapy despite vIGA-AD of '1-almost clear'. Periodic clinic visits will include assessments for clinical safety, tolerability, and disease severity.

Sample Size Justification:

The sample size will provide a sufficient number of subjects to evaluate the long-term safety of ARQ-151 cream 0.15% or ARQ-151 cream 0.05% over 24 or 52 weeks of treatment, and in combination with other studies will provide the development program with sufficient numbers of subjects to meet ICH E1A safety exposure goals.

Number of Patients (planned):

Up to approximately 1500 subjects are planned to be enrolled in this study.

Duration of Treatment:

Approximately 24 (Cohort-Week 24) or 52 weeks

Main Criteria for Inclusion:

1. For adult subjects: Participants legally competent to sign and give informed consent. For pediatric and adolescent subjects: Informed consent of parent(s) or legal guardian, and, if age appropriate, assent by the subjects, as required by local laws.
2. Males and females, ages 2 years and older. (Only subjects 18 years and older will be enrolled at sites located in the province of Québec in Canada.)
3. Subjects with atopic dermatitis who met eligibility criteria for and successfully completed ARQ-151-311 or ARQ-151-312 or ARQ-151-315 through Week 4, and are able and eligible to enroll into this long-term safety study on the Week 4 visit of the preceding study.
4. Females of childbearing potential (FOCBP) must have a negative urine pregnancy test at all study visits. In addition, sexually active FOCBP must agree to use at least one form of a highly effective or barrier method of contraception throughout the trial. The use of abstinence as a contraceptive measure is acceptable as long as this is a consistent part of a lifestyle choice and an acceptable backup method has been identified if the subject becomes sexually active.
5. Females of non-childbearing potential should either be pre-menarchal, or post-menopausal with spontaneous amenorrhea for at least 12 months (post-menopausal status would have been confirmed with FSH testing in the preceding study) or have undergone surgical sterilization (permanent sterilization methods include hysterectomy, bilateral oophorectomy, or bilateral salpingectomy).
6. Subjects and parent(s)/legal guardian(s) are considered reliable and capable of adhering to the Protocol and visit schedule, according to the judgment of the Investigator.

Main Criteria for Exclusion:

1. Subjects who experienced a treatment-related AE or a serious AE (SAE) that precluded further treatment with ARQ-151 cream in studies ARQ-151-311 or ARQ-151-312 or ARQ-151-315.
2. Subjects that use any Excluded Medications and Treatments (see [Table 2](#)).
3. Subjects with skin conditions other than AD that would interfere with evaluations of the effect of the study medication on AD, as determined by the Investigator. Subjects with any condition on the treatment area which, in the opinion of the Investigator, could confound efficacy measurements (e.g., molluscum contagiosum).
4. Subjects with known genetic dermatological conditions that overlap with AD, such as Netherton syndrome.
5. Known allergies to excipients in ARQ-151 cream
[REDACTED]
6. Subjects who cannot discontinue the use of strong cytochrome P-450 CYP3A4 inhibitors e.g., indinavir, nelfinavir, ritonavir, clarithromycin, itraconazole, ketoconazole, nefazodone, saquinavir, suboxone and telithromycin during the study period.
7. Subjects who cannot discontinue the use of strong cytochrome P-450 CYP3A4 inducers e.g., efavirenz, nevirapine, glucocorticoids, barbiturates (including phenobarbital), phenytoin, and rifampin during the study period.
8. Known or suspected:
 - a. Severe renal insufficiency (defined as calculated creatinine clearance < 30mL/min)
Refer to the creatinine levels from the following visits:
 - ARQ-151-311/ARQ-151-312 studies: Screening Visit for subjects ages 6-11 and Baseline/Day 1 for subjects \geq 12 years old (for subjects 12-18 years old, if screening lab tests were collected within 3 weeks of Baseline/Day 1, screening results will be used)
 - ARQ-151-315 study: Screening Visit
 - b. Moderate to severe hepatic disorders (Child-Pugh B or C)
 - c. History of severe depression, suicidal ideation or behavior
9. Females who are pregnant, wishing to become pregnant during the study, or are breast-feeding.
10. Subjects with any known serious medical condition (e.g., uncontrolled hypo- or hyper-thyroidism) or clinically significant laboratory abnormality that would prevent study participation or place the subject at significant risk, as determined by the Investigator.
11. Subjects with a history of chronic alcohol or drug abuse within 6 months of initiation of study medication.
12. Current or a history of cancer within 5 years with the exception of fully treated skin basal cell carcinoma, cutaneous squamous cell carcinoma or carcinoma in situ of the cervix.
13. Subjects and parent(s)/legal guardian(s) who are unable to communicate, read or understand the local language(s), or who display another condition, which in the Investigator's opinion, makes them unsuitable for clinical study participation.
14. Subjects who are family members of the clinical study site, clinical study staff, or sponsor, or family members of enrolled subjects (subjects enrolled in other studies of ARQ-151) living in the same house.

Investigational Product, Dosage and Mode of Administration:

For the first 4 weeks of study ARQ-151-313, all subjects will apply study medication QD in the areas identified and treated as per the body diagram in the preceding study (ARQ-151-311/312/315). Beginning at the Week 4 visit, any subject who achieves vIGA-AD of '0-clear' as confirmed by the Investigator at a scheduled or unscheduled clinic visit, will switch to twice weekly (BIW) maintenance treatment. For maintenance therapy, study medication will be applied on two nonconsecutive days per week (e.g. Monday and Thursday) to areas commonly and/or most recently affected by AD, and any areas where AD is developing. Subjects receiving maintenance treatment who experience AD worsening (signs and symptoms) for 1 week despite dosing twice weekly will phone the clinical study site, resume daily dosing, and complete the subject diary accordingly. The phone call (but not a clinic visit) is required to resume daily dosing. At clinic visits, subjects receiving maintenance treatment may continue twice weekly maintenance dosing if vIGA-AD is either '0-clear' or '1-almost clear'. Subjects will resume daily dosing if vIGA-AD ≥ 2 , and can resume daily dosing if signs/symptoms of AD are not adequately controlled with maintenance therapy despite vIGA-AD of '1-almost clear'.

Key Assessments:

Safety will be monitored through local tolerability assessments, vital signs, physical examination, safety labs (subjects ≥ 12 years old), Children's Depression Inventory 2 (CDI-2, parent report for children 6-11 years old, inclusive), modified PHQ-A (for adolescents 12-17 years old, inclusive), PHQ-8 (for adults), C-SSRS (for adolescents and adults of 12 years old and older), and AEs. Parents/caregivers of subjects 2 to 5 years of age will be advised to promptly report any changes in behavior that could signal psychological distress or emotional distress.

Efficacy assessments will include vIGA-AD, EASI, WI-NRS, BSA, CDLQI/DLQI, DFI, IDQOL, SCORAD, and POEM.

Study Endpoints:

Primary:

- Adverse Events (AEs)
- Serious Adverse Events (SAEs)

Secondary:

- Validated Investigator Global Assessment-Atopic Dermatitis (vIGA-AD) value 0 or 1 at each assessment
- vIGA-AD success (defined as vIGA-AD value of 0 or 1 plus a 2-grade improvement from baseline)
- WI-NRS score over time
- EASI score over time

Criteria for Evaluation:

Safety:

The safety population will include all subjects who are enrolled and received at least one confirmed dose of study medication.

Descriptive statistics will be calculated for quantitative safety data and frequency counts will be compiled for classification of qualitative safety data.

The subject incidence of treatment-emergent adverse events (TEAE) will be summarized overall, by severity, and by attribution.

Statistical Methods:

Descriptive statistics will be presented for the endpoints and safety data collected in the clinical trial. This includes the number and percentage of subjects for binary endpoints/categorical data, and mean, SD, median, Q1, Q3, minimum, and maximum for continuous data.

Adverse Events

For the primary endpoints, the occurrence of TEAEs and the occurrence of Serious Adverse Events (SAEs) will be tabulated by preferred term and system organ class.

In addition, summary tables of TEAEs by severity, by relationship to investigational product, and those leading to withdrawal from investigational product will be created.

Vital Signs

Descriptive statistics will be calculated for vital signs over time.

Clinical Laboratory Results

Descriptive statistics of the laboratory parameters will be calculated at each scheduled time point. Shifts from baseline will be tabulated.

[figure not shown]
Patient Health Questionnaires

CDI-2 (in 6-11 year-olds), PHQ-8 (in adults), a modified version of the PHQ-A (in adolescents), and C-SSRS questionnaires (in adolescents and adults) will be completed at all study visits. Descriptive statistics will be calculated for the CDI-2, PHQ-8, and Modified PHQ-A. The C-SSRS will be analyzed per the Scoring and Data Analysis Guide from the Columbia Lighthouse Project.

Efficacy Assessments

Descriptive statistics will be presented for the efficacy data collected in the clinical trial for the subjects who enroll in this study and receive at least one day of study drug. For the binary and continuous endpoints related to vIGA-AD, WI-NRS, and EASI, descriptive statistics will be provided for the endpoints each scheduled visit.

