2.4.1. Dose Selection

The doses included in this study are the same as those included in the base studies (ARQ-151-311, ARQ-151-312 and ARQ-151-315) in which the subjects initiated treatment. Subjects 6 years and older will be treated with ARQ-151 cream 0.15%, and subjects 2 to 5 years old will be treated with ARQ-151 cream 0.05%. The selection of these doses in the prior studies is supported by data from ARQ-151-212 and ARQ-151-105.

In ARQ-151-212 (conducted in adult and adolescent subjects), results for the primary efficacy endpoint, mean absolute change from baseline in EASI score at Week 4, were numerically higher in the ARQ-151 cream 0.05% and ARQ-151 cream 0.15% ($p=0.097$) groups than in the vehicle group. Furthermore, the result of the sensitivity analysis of the primary endpoint at Week 4 was statistically significant (ARQ-151 cream 0.15%, $p=0.027$). Statistical significance was reached for numerous other clinically important efficacy endpoints including percent change from baseline in EASI score, EASI-75 responders, and subjects achieving vIGA-AD score of clear or almost clear. Both doses of topical roflumilast (0.15% and 0.05%) had a similar and favorable safety and tolerability profile, with generally more favorable efficacy observed at the ARQ-151 cream 0.15% dose. Results of this study support the use of ARQ-151 cream 0.15% in further studies of adult and adolescent subjects with mild to moderate AD.

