4. INVESTIGATIONAL PLAN

4.1. Overall Study Design and Plan

This is a Phase 3, open-label, single-arm, long-term safety study in which ARQ-151 cream 0.15% or ARQ-151 cream 0.05% is applied QD x 24 (Cohort-Week 24) or 52 weeks to subjects with mild to moderate atopic dermatitis (except for time on BIW maintenance therapy).

- Eligible subjects will enroll into the long-term safety study on the same day as the Week 4 visit of the preceding study (ARQ-151-311 or ARQ-151-312 or ARQ-151-315).
- Subjects/caregivers will apply ARQ-151 cream 0.15% for subjects \geq 6 years old or ARQ-151 cream 0.05% for subjects 2-5 years old.
- If a 5 year-old subject turns 6 years-old during this study, the subject will be switched from ARQ-151 cream 0.05% to ARQ-151 cream 0.15% at his/her first scheduled post-birthday visit. Dose reduction back to 0.05% is not permitted.
- The study drug will be applied QD for 24 (Cohort-Week 24) or 52 weeks to all AD affected areas and any newly appearing AD lesions that arise during the study, except on the scalp (unless entering BIW maintenance therapy, as described below).
- **For the first 4 weeks of study ARQ-151-313, all subjects will apply study medication QD in the areas identified and treated as per the body diagram in the preceding study (ARQ-151-311/312/315).** Beginning at the Week 4 visit, any subject who achieves vIGA-AD of '0-clear' as confirmed by the Investigator at a scheduled or unscheduled clinic visit, will switch to twice weekly (BIW) maintenance treatment. For maintenance therapy, study medication will be applied on two nonconsecutive days per week (e.g. Monday and Thursday) to areas commonly and/or most recently affected by AD, and any areas where AD is developing. Subjects receiving maintenance treatment who experience AD worsening (signs and symptoms) for 1 week despite dosing twice weekly will phone the clinical study site, resume daily dosing, and complete the subject diary accordingly. The phone call (but not a clinic visit) is required to resume daily dosing. At clinic visits, subjects receiving maintenance treatment may continue twice weekly maintenance dosing if vIGA-AD is either '0-clear' or '1-almost clear'. Subjects will resume daily dosing if vIGA-AD \geq 2, and can resume daily dosing if signs/symptoms of AD are not adequately controlled with maintenance therapy despite vIGA-AD of '1-almost clear'.

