6. DATA ANALYSIS

Data will be handled and processed according to the Contract Research Organization's Standard Operating Procedures, which are written based on the principles of GCP.

Full details of the statistical analysis will be included in the Statistical Analysis Plan (SAP).

Data from this study may be analyzed prior to the final analysis for regulatory reporting purposes. Under Amendment 1, subjects 6-17 years of age that have completed the 4-week treatment period in ARQ-151-311 or ARQ-151-312 will be treated for 24 weeks with ARQ-151 cream 0.15% (Cohort-Week 24). The rest of the subjects will be treated for up to 52 weeks with ARQ-151. The analysis will be performed by cohorts and overall over time.

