3.4 Treatment

Initial treatment with the IP in the ARQ-151-313 will occur on Day 1 (Day 29 from the preceding study). Roflumilast cream 0.15% or roflumilast cream 0.05% is administered once daily (unless entering BIW maintenance therapy after Week 4) as a topical product to cover the skin surface at an application rate of approximately 2 mg/cm².

- Roflumilast cream 0.15%, QD (\geq 6 years old on Day 1 of ARQ-151-313)
- Roflumilast cream 0.05%, QD (2 -5 years old on Day 1 of ARQ-151-313)

Subjects who turn 6 years old during the study will switch to roflumilast cream 0.15% at their first scheduled post-birthday visit.

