5.1 Sample Size

Up to approximately 1500 subjects that have completed the 4-week treatment period in studies ARQ-151-311, ARQ-151-312, or ARQ-151-315 and are willing and qualified to enroll in this long-term extension study will receive roflumilast cream 0.15% (ARQ-151-311/312 roll-overs) or roflumilast cream 0.05% (ARQ-151-315 roll-overs) QD.

The sample size will provide a sufficient number of subjects to evaluate the long-term safety of roflumilast cream 0.15% or roflumilast cream 0.05% over 24 or 52 weeks of treatment (Cohort-Week 24 and Cohort-Week 52, respectively).

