Finally, in order to better understand the efficacy and safety profile of ARQ-151-315 rollover subjects who start this study 5 years old and who turn 6 years old during this study and so, will be switched from roflumilast cream 0.05% to roflumilast cream 0.15% at his/her first scheduled post-birthday visit, analyses will also be performed for this subgroup of subjects. The list of efficacy and/or safety endpoints for which analysis will be performed for this subgroup of subjects will be determined, finalized and approved before the final database lock of parent study ARQ-151-315.

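### Two rules, by parent study and by age, give different cream strengths to an ARQ-151-315 roll-over who is already 6 on OLE Day 1

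*Protocol*

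**What the plan says.** **Strength by parent study.** The synopsis (Study Population) says that subjects "will receive ARQ-151 cream 0.15% (ARQ-151-311/312 roll-overs) or ARQ-151 cream 0.05% (ARQ-151-315 roll-overs) QD". The schema text (Protocol 1.2, SAP 3.2) makes the same split, and SAP 5.1 repeats it: "or roflumilast cream 0.05% (ARQ-151-315 roll-overs) QD".

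**Strength by age.** Protocol 2.4.1 states: "Subjects 6 years and older will be treated with ARQ-151 cream 0.15"%, with 0.05% for ages 2 to 5. The primary objective, Protocol 4.1 and SAP 3.1 use the same age split. SAP 3.4 fixes the date at which age counts: the 0.15% line is for subjects at least "6 years old on Day 1 of ARQ-151-313".

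**Switch rule.** Protocol 4.1: "If a 5 year-old subject turns 6 years-old during this study, the subject will be switched" to 0.15% at the first planned visit after the birthday. It adds that a return to 0.05% is not allowed.

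**Treatment length.** The synopsis says: "Subjects 6-17 years of age enrolled under Amendment 1 will be treated for 24 weeks with ARQ-151 cream 0.15% (Cohort-Week 24"), without naming a parent study. Protocol 6, footnote t of the schedule (Protocol 1.3) and SAP 3.1 tie Cohort-Week 24 to ARQ-151-311 and ARQ-151-312. Protocol 6 continues: "The rest of the subjects will be treated for up to 52 weeks with ARQ-151".

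**Analysis.** SAP 6.6 plans a subgroup of "ARQ-151-315 rollover subjects who start this study 5 years old and who turn 6 years old during this study". SAP 11 reasons that subjects from a parent roflumilast arm carry on with an unchanged treatment at roll-over.

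**The concern.** The two strength rules agree for nearly every subject. They part for a 315 roll-over whose sixth birthday falls between 315 entry and OLE Day 1. On the written text, two sites could start identical children on different strengths, each with a passage to point to.

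Nothing later in the plan corrects this. A 6-year-old started on 0.05% has no birthday left to trigger the switch, and one started on 0.15% may not go back.

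If the age rule governs, a child treated with roflumilast 0.05% in 315 changes strength on Day 1. The subgroup meant to describe that change does not include the child, and SAP 11 would describe the treatment as unchanged.

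**Working it through.** The plan states no figure on this point. The study is descriptive (SAP 5.7 plans no hypothesis tests), so the main check is to set the passages side by side for one child: 5 at 315 entry, 6 on OLE Day 1.

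| Source | Strength on Day 1 |
|---|---|
| Synopsis (Study Population), Protocol 1.2, SAP 3.2, SAP 5.1 | 0.05% |
| Primary objective, Protocol 2.4.1, Protocol 4.1, SAP 3.1, SAP 3.4 | 0.15% |
| Switch rule (synopsis, Protocol 4.1, SAP 3.1, SAP 3.4) | does not apply: birthday before ARQ-151-313 |

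Such a child can exist because OLE Day 1 is the parent Week 4 visit (synopsis; Protocol 4.3). The sponsor dealt with the same kind of gap elsewhere. The DFI rule (Protocol 5.2.6) covers subjects who reach 18 before enrolling in 313, and the age-specific assessments and the EASI formula are tied to Screening of the preceding study. No matching sentence exists for strength.

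**Analysis coverage.** The SAP 6.6 subgroup requires age 5 at OLE start. The SAP 11 summary of days on each dose counts days in this study only, so a child on 0.15% from Day 1 shows no change. The 315 treatment groups (SAP 5) combine 0.05% and 0.15%.

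**Illustrative size.** Assumptions that are not in the documents:
- Ages at 315 entry are spread evenly over 2 to under 6 years, which is 4 × 365.25 = 1461 days. The 315 age range is itself inferred from Protocol 2.4.1 and the parent treatment listed in SAP Appendix 1.
- The gap from 315 entry to OLE Day 1 is 28 days (the parent treatment period) to 56 days (adding an assumed 4-week screening).
- Between 200 and 550 children roll over from 315. The upper value is 1500 − 400 − 275 − 275 = 550, using the increments in the Protocol's Summary of Changes.

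Share already 6 on Day 1 = gap / 1461:
- 28 / 1461 = 1.9%
- 56 / 1461 = 3.8%

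Expected number of children:
- 200 roll-overs: 200 × 28/1461 = 3.8 to 200 × 56/1461 = 7.7, so about 4 to 8
- 550 roll-overs: 550 × 28/1461 = 10.5 to 550 × 56/1461 = 21.1, so about 11 to 21

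Chance of at least one such child in the smallest case: 1 − (1 − 28/1461)^200 = 98%.

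For comparison, 252/1461 = 17% would turn 6 during the OLE by Week 36, the last dispensing visit, and 364/1461 = 25% by Week 52. Children already 6 on Day 1 would therefore be between 28/(28 + 364) = 7% and 56/(56 + 252) = 18% of all 315 roll-overs who reach 6. These counts include former-vehicle children.

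**The case against.** The parent-study wording stands only in overview text: the synopsis population, the schema and the sample-size paragraph. The sections that describe treatment use age, and footnote m of the schedule says that kits are expected to be dispensed by affected BSA and age, referring to an IP Handling Manual that is not among these documents. It is fair to say that divergent dosing at sites is possible on paper but not shown to be likely. Even so, the footnote does not remove the contrary statements.

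A reader might infer an equal conflict on treatment length, because the synopsis sentence on ages 6 to 17 would place this child in the 24-week cohort. The documents do not support that weight. One sentence omits the parent study, while Protocol 6, footnote t and SAP 3.1 all limit the cohort to 311/312. It reads as a drafting omission and touches only children enrolled under Amendment 1.

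A reader might also infer that these children are never analysed. They are: they remain in the pooled 315 groups and in the safety and efficacy summaries built on them. They are outside the dedicated switch subgroup only. That subgroup is coherent as a description of switches during the OLE, since a child on 0.15% from Day 1 has no 0.05% period within it.

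Finally, former-vehicle children who start on 0.15% have had no change of roflumilast strength. A switch group defined only by first use of 0.15% would wrongly include them.

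**Conclusion.** The strength conflict holds on the current text. For a 315 roll-over who turned 6 before OLE Day 1, the Protocol and SAP give two instructions, and no later rule resolves them. The missing 311/312 limit in the synopsis sentence on Cohort-Week 24 is a minor related point. The gap in SAP 6.6 matters only if the reconciled rule lets strength change on Day 1, and then only for children who received roflumilast 0.05% in 315.

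The group is probably small: about 4 to 21 children under the assumptions above. The number who actually change strength is lower by an unknown amount, because the parent allocation ratio is not given. The 550 behind the upper end is an inference: 1500 is an approximate ceiling, and the documents do not state how many subjects come from 315. The effect on pooled results is minor. What is at stake is one unambiguous rule for paediatric dosing and a correct description of exposure. This review takes no position on which strength or duration is right.

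**What to change.** 1. Reconcile the synopsis, Protocol 1.2, SAP 3.2 and SAP 5.1 with Protocol 2.4.1 and 4.1 and SAP 3.1 and 3.4, so that one rule fixes the strength for a 315 roll-over already 6 on Day 1. In the same edit, reconcile the synopsis sentence on ages 6 to 17 with footnote t, Protocol 6 and SAP 3.1, so that treatment length is also settled.
2. If that rule allows a change of strength on Day 1, extend the SAP 6.6 switch analysis, or add a separately shown group. It should cover 315 roll-overs who received roflumilast 0.05% in 315 or in the OLE and then started 0.15%, dated by the first actual 0.15% application, Day 1 included. Former-vehicle children who start directly on 0.15% stay out.
3. Correct the SAP 11 statement that roflumilast-arm subjects continue an unchanged treatment, so that it allows for any child whose strength changes on Day 1.

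The cost is a protocol clarification and a few SAP sentences, with no new data. The interim analyses exclude 315 roll-overs (SAP 1 and 6.3), and SAP 6.6 leaves the endpoint list for its switch subgroup open until before the final 315 database lock, so the SAP edit can be made with that list.
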